## **PROTOCOL SUMMARY - 2010**

### **A 20 City Urban Community Randomized Trial of STD Prevention**

#### **I. Introduction**

This document summarizes the protocol implemented in the Peruvian Urban Community Randomization Trial of STD Prevention (The Peru PREVEN Study) and includes protocol revisions over the course of this 10 year multi-component (“complex”) intervention. When the proposal was originally submitted to the Wellcome Trust/Burroughs Wellcome Fund Infection Awareness Initiative in 1999 in collaboration with the National Peruvian STD Program, the study was designed as a three arm trial; the outcomes were the combined prevalences of sexually transmitted infections (STI) in women in antenatal clinics and military recruits, and in female sex workers (FSW). However, as is often the case for complex interventions[1-3], a variety of circumstances led to modification of the protocol.

Between proposal submission and study initiation, the overall funding from the Wellcome Trust was reduced by 25%, post-election political changes resulted in the deterioration of the Peruvian National STD/HIV Control Program, military service became no longer obligatory, and HIV surveillance in antenatal care was separated from the National STD/HIV Control Program and then weakened. PREVEN Study leaders in Peru transitioned from the National STD/HIV Control Program to a base at Universidad Peruana Cayetano Heredia (UPCH). The study protocol was therefore re-designed to include two, rather than three arms, with outcome measures planned for random samples of the general population of young adults and female sex workers, rather than samples of antenatal women and military recruits. The major protocol changes were communicated to our Wellcome Trust Programme Officer, [name], on March 14, 2002.

The outcome measures were determined *a priori*, as documented in our trial summary presented to the DSMB in April, 2006, which is attached. Following suggestions by the DSMB, the analysis plan was modified to use two-tailed tests for all analyses and to use analyses that adjusted for baseline differences in STI prevalences between the intervention and control cities.

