#### PRIMARY ANALYSISAA

The unit of analysis will be the city (i.e., composite curable STI prevalence at the city level). This approach is appropriate since the sample size is approximately the same from city to city. The primary analysis of intervention efficacy will be based on the model

$$d_i^O = b_0 + b_1 d_i^B + \varepsilon_i \quad (M1)$$

where  $d_i^O$  is the difference in the primary composite STI endpoint [gonorrhea, chlamydia, vaginal trichomonas, and syphilis seroreactivity (RPR  $\geq 1:8$ , TP•PA confirmed)] between the intervention and control communities (control – intervention) of the  $i$ th pair in the final (2006) outcome survey,  $d_i^B$  is the corresponding difference in the baseline (2002) survey and  $\varepsilon_i$  is a random error. The hypothesis of interest is

$$H_0: b_0 = 0 \quad (\text{no intervention effect}) \quad (H1)$$

---

AA Primary and secondary analysis descriptions taken from “PREVENanalysisPlan\_23.01.07.doc” dated 1/24/07 and updated 3/18/09

Ha:  $b_0 \neq 0$  (intervention effect)

Note that if  $d_i^B$  was not included in the model, this analysis would be equivalent to a paired t-test. The  $d_i^B$  term is included in the model to control for differences in STI prevalence at baseline (which may occur in spite of the matching).

Least squares regression will be used for model fitting. The standardized test statistic  $\hat{b}_0 / se(\hat{b}_0)$  from this analysis has a t-distribution with 8 degrees of freedom. A p-value will be reported for the hypothesis (H1) and a type I error rate ( $\alpha$ ) of 0.05 (two-tailed) will be used to reject/fail to reject the null hypothesis (H1).

The endpoint in the primary analysis will be the composite curable STI endpoint [combined gonorrhea, chlamydia, vaginal trichomoniasis, or syphilis (RPR  $\geq 1:8$ , TP•PA confirmed)] as measured in the GP.

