## POWER CALCULATIONSBB

In Table 2 we present power calculations for testing for a 30-50% reduction in the primary STD outcomes between the treatment and control communities based on the random

---

BB Power calculations taken from “PREVEN trial summary.doc” dated 3/7/06 and presented for DSMB review in April 2006.

population survey of 600 men and women per city. The FSW population is considered separately. These calculations make use of the standard sample size/power formula for matched community randomized trials, as shown below.

$$n = 2 + \frac{(Z_{1-\alpha} + Z_{1-\beta})^2 \left[ p_1(1-p_1)/f + p_2(1-p_2)/f + k^2(p_1^2 + p_2^2) \right]}{(p_1 - p_2)^2}$$

In this formula  $p_1$  and  $p_2$  are the disease prevalences in the treatment and control communities, respectively,  $k$  is the coefficient of variation of disease prevalence between communities,  $f$  is the number of individuals per community and  $n$  is the number of communities. The Z's in the formula represent standard normal quantiles for appropriate type I and type II error rates. Disease prevalence in the control communities and the coefficient of variation are based on the baseline survey data.

Although the investigators cannot be formally blinded to the treatment assignments, only pooled results (over the two study arms) will be presented by the statistician at investigator meetings.

[figure not shown]
**Table 2. Power for comparing treatment ( $n = 10$ ) and control communities ( $n = 10$ ) given number per community, prevalence,  $\alpha = 0.05$  (1-tailed), coefficient of variation = .10 and indicated reduction in disease in treatment cities. Number of GPS results is reduced from 600 to 500 to allow for refusal to provide biologic samples.**

	Number per community			Percent reduction		
	General	FSW	Prev	30	40	50
	population			Percent	Percent	Percent
Any STD	500		.10	.99	.99	.99
		200	.14	.87	.98	.99
Chlamydia	500		.04	.86	.98	.99
Trichomonas	250		.05	.72	.92	.99
Syphilis	500		.01	.41	.63	.81
HIV	500		.005	.27	.40	.57

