### Open Session (from 9:00am to 12:30pm)

The following points were discussed in response to the presentations by the study team:

- Imbalance between treatment arms. It was noted that the unrestricted pair-matched randomization had resulted in a situation where baseline prevalences of the primary endpoint were generally higher in the intervention cities than their matched controls.
- Clarification of cluster classification. It was noted that in one of the matched pairs, the control city did not belong to the same geographical region as the corresponding intervention city, although STI prevalences were similar.
- Mobility of FSW. It was noted that mobility of the FSW was high, raising concerns over dilution of measured intervention effects. Mobility also poses challenges to delivery of the intervention, but these are likely to be realistic constraints, typical of many FSW settings.
- Inclusion of male sex workers (MSW). The study team reported that MSW are now being included in the intervention and that some evaluations are planned, although not as a formal part of the current trial.
- Prescription by pharmacists and self-medication. DSMB members asked if pharmacists are allowed to prescribe antibiotics in Peru. The team responded that, while this is not legally permitted, it is very common for pharmacists and non-pharmacist drug-store clerks to provide many kinds of drugs, antibiotics included, without prescription. DSMB members also asked about self-medication as could be practiced by FSW.
- Process evaluation of RED PREVEN intervention. It was noted that process measures for UD were generally better than for GU. The team commented that this may reflect long-standing public perceptions in Peru of UD as an STD, while this is less the case for GU.
- Changes in survey methods. The study team reported that survey methods had been modified for the outcome survey, particularly to improve the phrasing of questions and to implement PDA-based questionnaires. It was agreed that, while changes in methods during a trial should generally be avoided, in this case the benefits outweighed the risks. The primary analysis in this trial relates to comparisons between treatment arms at follow-up, rather than direct comparison of outcome versus baseline measurements.

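### Table 2 still gives power for a one-tailed normal test, though the plan now tests two-tailed on t with 8 df; 12 of 18 cells are too high, almost all in secondary rows

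*Supplement*

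**What the plan says.** The 2010 protocol summary, section III, sets out the power calculation in these terms: "These calculations make use of the standard sample size/power formula for matched community randomized trials, as shown below". It adds: "The Z's in the formula represent standard normal quantiles for appropriate type I and type II error rates". The caption of Table 2 fixes alpha at 0.05 "1-tailed), coefficient of variation = .10 and indicated reduction in disease in treatment cities". Footnote BB says the calculation comes from a trial summary dated 3/7/06, presented to the DSMB in April 2006.

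Under Primary analysis, the same section says of the standardized estimate of b0 in model M1 that it "from this analysis has a t-distribution with 8 degrees of freedom", and that a type I error rate of "0.05 (two-tailed) will be used to reject/fail to reject the null hypothesis (H1"). Secondary analysis applies this to the FSW composite and to the individual infections. The latest Data Analysis Plan (Inferential analyses) repeats the test and also lists HIV.

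The Introduction explains the change: following the DSMB's suggestions, "the analysis plan was modified to use two-tailed tests for all analyses".

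**The concern.** The power table and the planned test sit in one section and describe different tests. The sidedness changed after the table was made, and the table was reprinted without being recomputed and without a note that it predates the change. Power for a one-tailed test at 0.05 is higher than for a two-tailed test at 0.05, so the stated figures are not those of the test that will be run.

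What is at stake is how null results are read. Someone who sees no effect on chlamydia, trichomonas, syphilis or HIV will use Table 2 to judge how much that means, and will credit the trial with more sensitivity than it had.

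**Working it through.** **Inputs (all from Table 2, its caption and its formula).** 10 matched pairs; k = 0.10; relative reductions of 30, 40 and 50%. Numbers per city (f) and control prevalences: general-population (GP) composite 500, .10; FSW composite 200, .14; chlamydia 500, .04; trichomonas 250, .05; syphilis 500, .01; HIV 500, .005.

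**Step 1: reproduce the printed table.** Let p be the control prevalence, q = p(1 − reduction), and

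V = q(1−q)/f + p(1−p)/f + k²(p² + q²).

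The printed formula, solved for power with n = 10 (so n − 2 = 8), is

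power = Φ(√8 · (p − q)/√V − z), with z = 1.645 one-tailed.

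Worked case, chlamydia at 30%: p = .04, q = .028.

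- V = .0000544 + .0000768 + .0000238 = .0001551
- (p − q)/√V = .012/.01245 = .9636
- √8 × .9636 = 2.726
- Φ(2.726 − 1.645) = .860. Printed: .86.

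One-tailed z reproduces 17 of the 18 cells within 2 points, reading values above .99 as .99. The exception is FSW at 30%: √8 × .042/√.001336 = 3.250, and Φ(3.250 − 1.645) = .946, against .87 printed. (FSW at 40% computes to .998 against .98 printed, just inside the tolerance.) So Table 2 is a one-tailed normal calculation.

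**Step 2: change the sidedness only.** With z = 1.960, chlamydia at 30% becomes Φ(2.726 − 1.960) = .778.

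**Step 3: the planned test.** Noncentral t with 8 df, two-tailed 0.05 (critical value 2.306), noncentrality √10 · (p − q)/√V. For chlamydia at 30% the noncentrality is 3.047 and the power .761.

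| Row | Stated 30/40/50% | Two-tailed z | Two-tailed t, 8 df |
|---|---|---|---|
| GP any STD | .99/.99/.99 | .98/>.99/>.99 | .97/>.99/>.99 |
| FSW any STD | .87/.98/.99 | .90/.99/>.99 | .89/.99/>.99 |
| Chlamydia | .86/.98/.99 | .78/.96/>.99 | .76/.955/>.99 |
| Trichomonas | .72/.92/.99 | .61/.87/.98 | .59/.85/.97 |
| Syphilis | .41/.63/.81 | .30/.50/.72 | .29/.49/.70 |
| HIV | .27/.40/.57 | .17/.29/.44 | .17/.28/.43 |

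**Step 4: count.** In the last column 12 of 18 cells lie below the stated value: GP composite at 30%, chlamydia at 30 and 40%, and all three cells for each of trichomonas, syphilis and HIV. Ten of these fall by more than 2 points, from 2.5 (chlamydia at 40%) to 14 (syphilis at 40%, HIV at 50%). The other two, GP composite at 30% and trichomonas at 50%, fall by 1.9. Two cells cross 80%: chlamydia at 30% and syphilis at 50%.

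**Step 5: what drives the loss.** Sidedness takes chlamydia at 30% from .860 to .778; moving to t with 8 df takes it only to .761. Across the table the second step costs about 0 to 2 points, because the added 2 in the printed formula already works as a small-sample allowance.

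**The case against.** The strongest reply is that nothing is hidden and little turns on it. The caption prints the sidedness, footnote BB dates the calculation before the April 2006 DSMB meeting, and the Introduction reports the later change. The 2010 document summarizes a trial already carried out, so no sample size, test or endpoint would change. HIV is already printed below 80% at every reduction, and syphilis is already printed as weak at 30 and 40%. All of this stands, and it limits the point to a reporting correction. It does not make the figures right: a reader who takes the powers from the table gets values the planned test does not have.

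Three stronger readings are tempting, and the documents do not support them.

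- *That the primary analysis is underpowered.* It is not, on the table's inputs: the GP composite keeps about .97 at 30% and more than .99 beyond.
- *That every row is overstated.* The FSW row is not: .87 at 30% lies below both the one-tailed value (.946) and the planned-test value (.89). That cell has a different fault, and its cause cannot be recovered from the documents.
- *That baseline imbalance lowers power by a known further amount.* In M1, Var(b0) = σ²(1/10 + mean(d_B)²/Sxx), where Sxx is the sum of squared deviations of the ten d_B from their mean. A non-zero mean baseline difference therefore widens the standard error, and the DSMB report does record that "baseline prevalences of the primary endpoint were generally higher in the intervention cities than their matched controls". But the documents give neither the mean nor the spread of d_B. Also, σ² here is the residual variance after regression on baseline, which may be smaller than the unadjusted variance in Table 2. The two effects pull in opposite directions and the net result is unknown. Any figure for an assumed imbalance would be an assumption and has no place in a restated table.

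**Conclusion.** The point holds as a mismatch between a table that was not updated and the current test. Where it matters, it matters for secondary outcomes: chlamydia no longer reaches 80% at a 30% reduction, syphilis no longer does at 50%, and trichomonas at 30% drops from .72 to .59. The primary composite loses about 2 points in one cell. The change from one-tailed to two-tailed accounts for nearly all of the loss.

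These figures rest on the table's own prevalences and numbers per city, on k = 0.10, and on the unadjusted pair variance. They take no account of any gain from baseline adjustment or any cost of baseline imbalance.

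**What to change.** 1. Recompute Table 2 for the two-tailed 0.05 test on t with 8 df and change the one-tailed label in the caption. At the table's own inputs, the replacement values are those in the last column above.
2. State that syphilis does not reach 80% power at a 50% reduction, that chlamydia does not at 30%, and that the primary composite stays at about .97 or higher.
3. Correct the FSW cell at 30%, or document the inputs that produced .87.
4. Mention the effect of baseline imbalance on Var(b0) in words. If a figure is wanted, compute it from the observed baseline differences together with the residual variance of M1.

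The cost is a re-run of one table and a few sentences. Most of the single-infection and HIV figures become less favourable. Design, test and endpoints stay as they are.

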## MATHEMATICAL MODELS

Mathematical models will be used to help distinguish the effect of different aspects of the interventions on the epidemiology of the different STDs. Data collected within the proposed studies and in other studies within Peru (e.g., 1996, 2000, and 2004 DHS surveys) on social, demographic, and behavioral variables (including number of sexual partnerships, frequency of unprotected sex, and patterns of sexual mixing) will be used by Imperial College investigators to develop quantitative models of STD transmission that will aid in understanding the epidemiology of STD in Peru. The observed risk behaviors of sex workers and their clients, and the proportion of young men using FSW, will be included in models to determine relative contributions of treatment versus behavior change. Meta-population models describing the transmission of STDs within and between cities will be developed to determine the importance of geographic reservoirs in maintaining the infections within the population. One hypothesis we

will explore is that more isolated communities will be less prone to reintroduction of infections, making interventions more successful.

*We employed modeling to assess the potential impact of the proposed interventions on STD rates in the population. We assume the pharmacy-based intervention decreases the mean duration of symptomatic infections to 2 weeks for 70% of men and women while the CSW intervention decreases the mean duration of asymptomatic infections in sex workers to 2 months i.e., the sex workers are screened on average 2 months after becoming infected. These results (Figure) support the proposed 3-year intervention period.*

#### **IV. Human subjects considerations**

##### ETHICAL REVIEW

Subsequent to initial review and approval, the responsible local IRBs or Ethical Committees (UPCH, UW, and NMRCD) reviewed the study annually. The investigators made safety and progress reports to the IRBs/ECs annually, and will report within three months of study termination or completion. These reports included the total number of participants enrolled in the study, all changes in the research activity, and all unanticipated problems involving risks to human subjects or others.

##### INFORMED CONSENT

To protect anonymity, participants provided verbal rather than written informed consent to complete a questionnaire and to provide biological specimens for STD/HIV testing. Consent also asked permission to keep specimens for future studies. The interviewers recorded in the consent process guide whether the participant agreed to provide questionnaire data and/or samples for the study, and whether they consented for HIV testing and/or storage of samples

for future studies. This information was transferred to electronic databases that are used to verify that each specimen collected has a valid informed consent form for the study, before the diagnostic tests are performed.

### CONFIDENTIALITY

All data are anonymous. We did not collect names of individuals or ask for signatures. Documents and specimens were labeled with consecutive alphanumeric codes, with prefixes indicating population and city, and suffixes indicating the type of document or specimen. Participants were given a card with their codes and instructions of where and when to go to seek their test results and additional counseling anonymously at a regional health center. As per the Peruvian law, participants received face-to-face counseling at the health centers before receiving test results.

### RISKS AND BENEFITS

Study participants may experience the following:

- Discomfort during phlebotomy. Participants may experience minor pain, bleeding, and/or bruising at the venipuncture site, and/or vasovagal reactions. Some participants may experience lightheadedness.
- Embarrassment and concern when answering questions about risk factors of HIV and STD infection. Subjects may choose to not answer any question that makes them feel uncomfortable.
- Distress at finding out that they have HIV or another STD. All participants will receive pre-test and post-test counseling.
- Discrimination if others learn participants' HIV status. To help protect human subjects, all study staff will receive training in safeguarding confidentiality as well as in the

protection of human subjects. All information on participants will be kept extremely confidential and will not be shared with non-investigators.

- Other unforeseen potential harms: Although potential harm to participants in this study is expected to be minimal, the known risk will be thoroughly explained to participants as part of the informed consent process.

[figure not shown]
Although adverse events in this study are expected to be uncommon, the known risks are still thoroughly explained to participants as part of the informed consent process. All interviewers, counselors, and laboratory technicians record any unforeseen adverse event in their daily activity log and report it to their supervisors/coordinators. The supervisors/coordinators generate electronic reports via the study's web page. The report is accessible to the core team which reports it to the local IRB/EC.

Benefits include receiving screening and treatment if indicated for STIs. Pharmacy staffs receive training to improve management of STIs and referrals. The FSW intervention improves coverage and services to a high-risk group who usually do not have access to high quality care. If the model proves effective, the intervention could be expanded to other cities. Participants for both surveys are not monetarily reimbursed, but instead receive small gifts (study caps and T-shirts for GPS participants, and 15 condoms for FSW survey participants) as compensation for their participation.

## **V. Timeline**

We initially planned to maintain the interventions for 2.5 years, but with additional funding from the Wellcome Trust, and upon recommendation from the DSMB, we were able to continue the PREVEN Network and FSW mobile team interventions for approximately 40 months, including six months of scale-up of these interventions, and 36 months of the full

intervention.CC Interim surveys were completed in Year 3 and final outcome surveys were completed in Year 5.

[figure not shown]
CC Updated timeline with additional grant funding from Wellcome Trust Health Consequences of Population Change (UW IRB Approval 8/11/2006)

## Appendix A: Laboratory Flow Charts

### *Chlamydia: 2002*

[figure not shown]

#### Definitions

**Positive** – Positive in the Roche assays or positive in the Aptima assay performed on the 2SP-suspended specimen from individuals indeterminate in the Roche assay.

**Negative** – Initially negative in the Roche assay or negative in the Aptima assay subsequently performed on the 2SP-suspended specimen.

**Gonorrhea: 2002**

[figure not shown]

**Definitions**

**Positive** – Positive in both the Aptima and Roche assays or positive in the Aptima assay performed on the 2SP-suspended specimen from individuals indeterminate in the Roche assay.

**Negative** – Initially negative in the Roche assay or negative in the Aptima assay subsequently performed on the 2SP-suspended specimen.

*Chlamydia and Gonorrhea: 2006*

[figure not shown]

**Definitions**

**Positive** – Initially positive in both the Aptima and Roche assays or positive in the Aptima assay performed on the 2SP-suspended specimen from individuals positive or equivocal in the Aptima assay and negative or indeterminate in the Roche assay.

**Negative** – Initially negative in the Aptima assay or negative in the Aptima assay subsequently performed on the 2SP-suspended specimen.

Trichomoniasis

